## **Data and Patient Safety Monitoring Plan**

All data will be maintained by the primary investigator in a locked office and password-protected computer.

At each contact with the subject, the study team must seek information on adverse events by specific questioning and, as appropriate, by examination. Information on all adverse events should be recorded immediately. All clearly related signs, symptoms and abnormal diagnostics should be recorded.

#### **Recording of Adverse Events:**

All adverse events occurring during the study period will be recorded. Adverse event data collection will begin the moment informed consent is signed. The clinical course of each event will be followed until resolution, stabilization, or until it has been ultimately determined that the study treatment or participation is not the probable cause.

When an adverse event has been identified, the study team will take appropriated action necessary to protect the study participant and then complete the necessary paperwork and/or log. The sponsor-investigator will evaluate the event and determine the necessary follow-up and reporting required.

## **Survey Assessments:**

- 7 point VAS for pain
- Hip Disability and Osteoarthritis Outcome Score (HOOS)
  - Western Ontario and McMaster Universities Arthritis Index (WOMAC), calculated as a subscore from HOOS
- Patient Reported Outcome Measurement Information System (PROMIS) Global Health Scale

#### **Compensation:**

Patients will be compensated 25 dollars at the initial visit, and 10 dollars at each follow-up visit. This will be provided in the form of a Visa gift card mailed to the patient's home address.

#### **Data Analysis:**

The study sample size is based upon power calculations for change in pain score data from a previous study by our group in patients with FAI. To detect a difference in the change in pain between the first and last visit of 1.7 units, on a 7-point pain scale, using a power of 80% and  $\alpha$ =0.05, requires at total N of 32, or 16 per group. To account for 20% of patients who might withdraw, we will recruit 8 additional subjects for a total of 40 patients. We will use a mixed-effects linear regression model to look at the changes in individual parameters at multiple time points over the course of the study, as well as the associations between changes of multiple parameters. Independent variables in the model are treatment assignment and time, dependent

variables are outcomes scores, biomarkers and Kellgren-Lawrence scores. First, we will perform univariate and univariable models to explore the relative importance of each predictor variable followed by a stepwise procedure in which we will include all significant variables in multivariable model followed by dropping the highest non-significant variable (significance will be set at p=0.10) until only significant variables remain. This will be repeated for each dependent variable. The robustness will be tested by performing model fitting and examining residual plots.

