## **Methods:**

#### **Inclusion Criteria:**

- Patients with symptomatic FAI with duration of symptoms for at least 6 weeks
- Clinical and radiographic evidence of FAI defined as the presence of a cam, pincer or combined lesion apparent from radiographs
- Mild to moderate osteoarthritis (Kellgren-Lawrence grade  $\leq 2$ )
- Patients able to provide consent to study participation
- VAS pain level of  $\geq 5$

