## Follow-up Visits:

Subjects will return to the clinic at 6 weeks, 3 months, 6 months and 12 months. At each visit, the following will be performed:

- Physical exam;
- 7 point visual analog pain scale;
- the WOMAC, the HOOS, and the PROMIS Global Health scale;
- Hip Radiographs including standing AP pelvis, lateral Dunn views, and false profile view (initial encounter and at 12 months only);
- serum biomarkers (IFN-g, IL-6, MCP-1, MIP-1b, IL-1b, TNF-alpha, highly sensitive CRP, COMP) at all time points; and
- any adverse events, regardless of severity

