# **Potential Pitfalls and Limitations:**

The study team has extensive experience studying FAI in patients in our MedSport clinic at the University of Michigan. All techniques and methodologies are currently in use and have previously been published in top orthopaedic journals. The main limitation we perceive is recruiting a sufficient number of subjects to the study. However, we have a high volume of patients pursuing treatment for FAI and anticipate it would be easy to recruit subjects into the study. While we think that a mixed-effects linear regression model is appropriate and informative for this study, an alternative approach would be a two-way repeat measures ANOVA. Given the statistical expertise of the study team, we do not anticipate any problems in performing analyses.

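### The within-patient covariance and the 12-month treatment contrast are not specified, so the standard error of the pain change that the trial is sized on could be wrong in either direction.

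*Combined protocol and SAP*

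**What the plan says.** - **Model.** The Data Analysis section states: "We will use a mixed-effects linear regression model to look at the changes in individual parameters at multiple time points". Treatment assignment and time are the independent variables. The section names no random effects, residual covariance, type of standard error, degrees-of-freedom method or treatment-by-time term, and the model is to be repeated for each dependent variable.
- **Check.** "The robustness will be tested by performing model fitting and examining residual plots".
- **Alternative.** Potential Pitfalls and Limitations says that "an alternative approach would be a two-way repeat measures ANOVA". No sphericity check or correction is mentioned.
- **Schedule.** Follow-up Visits: "Subjects will return to the clinic at 6 weeks, 3 months, 6 months and 12 months". With baseline (Data Collection section) that makes five unevenly spaced measurements.
- **Sizing contrast.** "To detect a difference in the change in pain between the first and last visit of 1.7 units, on a 7-point pain scale", at 80% power and two groups of 16 ("0.05, requires at total N of 32, or 16 per group").
- **Entry rule.** The Inclusion Criteria require a "VAS pain level of" 5 or more.

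**The concern.** A patient random intercept with constant residual variance is the simplest model that fits the plan's wording. It gives every pair of visits the same correlation. It therefore estimates the variance of a baseline-to-12-month change by pooling all ten visit pairs, most of them much closer together than 12 months. If correlation fades with time, the pooled figure is too small for the longest gap, and the interval and p-value for the sizing contrast are too optimistic. A repeated measures ANOVA with pooled error behaves the same way for this contrast.

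The entry rule adds a second departure. Restricting pain at baseline but not later makes equal variance across visits doubtful, and this tends to offset the first effect or reverse it. The direction of the error therefore cannot be known in advance. Ordinary residual plots would not reveal a wrong correlation structure.

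**Working it through.** **The plan's own figure.** The documents give no SD for the pain change, so the evaluable total of 32 cannot be reproduced, only solved backwards. For 16 per group and two-sided 5% (sidedness is not stated), SD = 1.7 × √(16/2) / (1.960 + 0.842) = 1.72; with the t distribution it is about 1.66. The dropout step agrees: 32 / 0.80 = 40.

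**Inputs.** Visits at 0, 1.5, 3, 6 and 12 months, and 16 evaluable patients per arm, come from the documents. All correlations and relative SDs below are assumptions.

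**Formulas**, for balanced complete data with a treatment-by-visit term:

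- Variance of the 12-month change used by a random-intercept fit or pooled-error ANOVA: 2 × (mean variance − mean covariance).
- True variance: var(0) + var(12) − 2 cov(0,12).
- SE ratio = √(model / true).
- Approximate type I error = 2 × [1 − Φ(1.96 × ratio)].

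**Example 1: equal variances, correlation decaying exponentially in time to 0.5 at 12 months.** The ten pairwise correlations are 0.917, 0.841, 0.707, 0.500, 0.917, 0.771, 0.545, 0.841, 0.595 and 0.707, with mean 0.734. Ratio = √((1 − 0.734)/(1 − 0.500)) = √0.532 = 0.729, so the SE is 27.1% too small. Type I error = 2 × [1 − Φ(1.429)] = 15.3%. With the back-solved SD of 1.66, the true SE of the arm difference is 1.66 × √(2/16) = 0.587, and the model would report 0.729 × 0.587 = 0.428.

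**Example 2: baseline SD half the later SD, all correlations 0.5.** Mean variance = (0.25 + 4 × 1)/5 = 0.85. Mean covariance = (4 × 0.25 + 6 × 0.50)/10 = 0.40. Model = 2 × 0.45 = 0.90; true = 0.25 + 1 − 2 × 0.25 = 0.75. Ratio = √1.2 = 1.095, so the SE is 9.5% too large and type I error is 3.2%.

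**Range**

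| Assumed truth | Equal variances: SE error, type I | Baseline SD halved: SE error, type I |
|---|---|---|
| Autoregressive by visit, 0.5 | −14.0%, 9.2% | −0.3%, 5.1% |
| Autoregressive by visit, 0.7 | −20.5%, 11.9% | −8.9%, 7.4% |
| Autoregressive by visit, 0.9 | −26.5%, 15.0% | −19.9%, 11.7% |
| Exponential in time, 0.3 at 12 months | −24.3%, 13.8% | −11.3%, 8.2% |
| Exponential in time, 0.5 at 12 months | −27.1%, 15.3% | −16.1%, 10.0% |
| Equal correlation 0.5 | 0%, 5.0% | +9.5%, 3.2% |

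With equal variances, weaker correlation gives less (autoregressive 0.3: 7.6% too small). Exponential decay approaches 31% too small (type I error about 18%) as correlations approach one. An illustrative random-slope truth reached 37%.

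**Simulation** (16 per arm, normal complete data, no treatment effect, 20,000 trials per scenario) agreed with these type I errors to within one percentage point. In the same scenarios:

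- a t-test on the 12-month change stayed at 4.7% to 5.6%;
- the additive treatment effect, with no interaction, stayed at 4.8% to 5.1%;
- the overall treatment-by-time F test of the ANOVA was at about 6% to 8% under decay.

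**The case against.** A reader might infer that the plan commits to a random-intercept model, and that its error bar is therefore too narrow by up to some fixed amount such as 27%. The documents do not support that, for five reasons, all of which stand.

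- The plan does not say random intercept. Random slopes, a structured residual covariance or robust errors would all fit its wording. The supportable criticism is that valid and invalid analyses both fit the text, so the choice is open until the data are seen.
- Read literally, the model is additive in treatment and time. With complete data that treatment test compares patient means and is valid under any correlation pattern. But it does not estimate the difference in first-to-last-visit change on which the trial is sized. Delivering that needs a treatment-by-time contrast, and that is where the standard error matters.
- The figure of 27% is one assumed scenario, not a bound. Other assumptions give more, less, none, or an interval that is too wide.
- The entry rule is not further evidence of too small a standard error. If the threshold refers to the 7-point scale with a maximum of 7, which the Inclusion Criteria do not say, entry scores span only 5 to 7 and the baseline SD can hardly exceed 1. That works against the effect of decaying correlation.
- Not every analysis is exposed. ANOVA needs sphericity, which is weaker than equal correlation, and its overall interaction test is only mildly affected. Kellgren-Lawrence is graded at two visits, so there is only one visit pair and nothing to pool wrongly.

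What remains is an unspecified choice that decides whether the sizing contrast has a valid standard error.

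**Conclusion.** The point holds as a conditional one: the covariance structure and the 12-month contrast need to be stated. If the contrast comes from a random-intercept fit or a pooled-error ANOVA, the error under the assumptions tabulated runs from about 27% too small, or about 31% at the limit of simple decay, to about 9% too large. Type I error runs from about 15% (18% at that limit) down to 3%. Equal correlation with equal variance gives no error. None of these figures can be narrowed from the documents, and all assume complete data although 20% withdrawal is planned for. This is a change that should be made: it costs little and makes the 12-month contrast valid whichever way the error would have gone.

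**What to change.** **Data Analysis.** For outcomes measured at all five visits, specify:

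- visit as a categorical factor;
- a treatment-by-visit term, with the 12-month contrast in change from baseline as the primary test for pain;
- an unstructured within-patient covariance, fitted by REML with Kenward-Roger (or Satterthwaite) degrees of freedom;
- a heterogeneous autoregressive structure as the named fallback if the unstructured fit does not converge.

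**Potential Pitfalls and Limitations.** Replace the repeated measures ANOVA with a t-test or ANCOVA on the 12-month change. At the least, add a sphericity correction and an error term specific to that contrast.

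**Cost.** Wording only, with no extra patients or visits. The unstructured model estimates 5 × 6 / 2 = 15 covariance parameters against 2 for a random intercept, and intervals may be somewhat wider. Whether the resulting precision matches what the sample size assumed cannot be checked, because no SD is given; stating that SD would allow it.

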#### Risks:

Standard risks involved with intra-articular hip injection including bleeding, infection, nerve damage, increased pain, reaction to anesthetic.

For Kenalog, complications are infrequent, though some mild local complications may occur, as listed in the FDA approved label dated June 2011. Some of these are atrophy of the skin at the injection site, facial flush, and post-injection flare (soreness and inflammation following the injection). Systemic side effects such as infection, increased blood glucose, hypercortisolism, and others are rarely seen. There is a rare risk of anaphylaxis, including death

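### One p=0.10 stepwise procedure serves both the randomised comparison and the association analysis: its predictor list conflicts with its aims, and the treatment term is not protected

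*Combined protocol and SAP*

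**What the plan says.** The Data Analysis section states: "We will use a mixed-effects linear regression model to look at the changes in individual parameters at multiple time points". The same sentence adds a second purpose, "as well as the associations between changes of multiple parameters". The next sentence fixes the roles: "Independent variables in the model are treatment assignment and time", while the dependent "variables are outcomes scores, biomarkers and Kellgren-Lawrence scores".

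The model is then built by selection. Univariable models are to "explore the relative importance of each predictor variable followed by a stepwise procedure". After that, "we will include all significant variables in multivariable model", and the least significant term is removed repeatedly until every remaining term meets p=0.10. The procedure applies to each dependent variable in turn, so it covers VAS pain, the primary outcome.

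The section sets out no separate model for the randomised comparison, does not force treatment to stay in, names no treatment-by-time interaction, and gives no list of candidates for selection beyond treatment and time. Potential Pitfalls and Limitations adds only a two-way repeated-measures ANOVA as an alternative.

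Two other places bear on the point. Follow-up Visits schedules eight serum markers at every time point, so most marker values are taken after injection. Hypothesis 2 expects PRP to lower circulating markers relative to corticosteroid; two of those it names, CRP and COMP, are on the measured list.

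**The concern.** The stated predictors do not fit the stated aims. A model with only treatment and time cannot say how the change in one parameter relates to the change in another; that needs a second parameter as a predictor. A univariable screen followed by multivariable elimination also means little with two predictors. An analyst who wants to carry out the whole paragraph would have to look for further candidates, and the only ones named are the other scores, the biomarkers and the Kellgren-Lawrence grades. No sentence addresses whether their post-injection values may enter a model that also holds treatment.

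Two things are at stake. First, on any reading, the randomised treatment term is subject to selection and may be missing from the final pain model. Second, if a post-injection marker enters alongside treatment, the treatment coefficient becomes the difference not accounted for by that marker. That is a different quantity from the total effect that randomisation protects and that the sample size was set to detect. Two analysts could follow different readings, report different primary results, and both claim to have followed the plan.

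**Working it through.** **Inputs from the documents (Data Analysis).** Difference in change in pain 1.7 units; power 80%; alpha 0.05; 16 per group; 20% withdrawal; selection at p=0.10.

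**Assumptions.** Two-sided test (sidedness is not stated). SD of change back-solved, because the plan cites its source but not its value. Marker shift between arms and within-arm marker-pain correlation are assumed throughout; the documents give neither.

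**1. The plan's own figures.** The withdrawal allowance reproduces: 32/(1 − 0.20) = 40. The 32 cannot be reproduced without the SD, but it can be inverted. Normal approximation: SD = 1.7 × √(16/2)/(1.96 + 0.84) ≈ 1.72. With the t test on 30 degrees of freedom, 80% power requires SD = 1.66, a standardised effect of 1.7/1.66 = 1.02. The 1.66 is used below.

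**2. Literal reading (treatment and time only).** Treatment is lost whenever its p-value is 0.10 or more. With noncentrality 1.7/(1.66 × √(2/16)) = 2.90 on 30 degrees of freedom, that probability is 11.8%. So about 12% of trials with the full design effect would end without a treatment term. In simulation, the mean estimate among trials that keep the term is about 1.8 rather than 1.7.

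**3. What the coefficient becomes if a marker change is admitted.** With treatment and marker both in the model:

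adjusted effect = 1.7 − 1.66 × correlation × shift

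- Shift 0.5 SD, correlation 0.3: 1.7 − 0.25 = 1.45
- Shift 0.8 SD, correlation 0.5: 1.7 − 0.66 = 1.04
- Shift 1.02 SD, correlation 0.5: 1.7 − 0.85 = 0.85
- Shift 1.02 SD in the opposite direction, correlation 0.5: 1.7 + 0.85 = 2.55

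If the shift or the correlation is zero, nothing is subtracted.

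**4. Power under the plan's selection rule.** Simulation of 3,000 to 4,000 trials per setting, with one change score per patient and least squares as a stand-in for the mixed model: screen at 0.10, then backward elimination at 0.10. Power is the chance that treatment is in the final model with p<0.05.

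| Marker shift (SD) | Correlation | Power | Treatment dropped |
|---|---|---|---|
| 0 | 0 | 81% | 12% |
| 0.5 | 0.3 | 72% | 20% |
| 0.5 | 0.5 | 66% | 25% |
| 0.8 | 0.3 | 60% | 31% |
| 0.8 | 0.5 | 47% | 40% |
| 1.02 | 0.3 | about 55% | about 37% |
| 1.02 | 0.5 | about 32% | about 58% |
| 1.02, opposite direction | 0.3 to 0.5 | 80 to 82% | – |

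At a shift of 0.2 SD, power is 76 to 78%.

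**5. False positives.** With no true pain effect, marker shifts of 0.5 to 1.02 SD and correlation 0.3 to 0.5, rejection under the plan's rule is 3.3 to 5.0%, near 4%. Treatment rarely passes its own univariable screen, so it is seldom in the final model to be tested.

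**6. Associations without treatment in the model.** If two parameters are unrelated within arms but each shifts by 1.02 SD, the pooled correlation is (1.02²/4)/(1 + 1.02²/4) = 0.26/1.26 = 0.21. That is purely a difference between arms, which is why an association model should keep treatment.

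**The case against.** The strongest reply is that the plan does say what the predictors are. It lists treatment and time, puts the biomarkers on the other side of the equation, and models each outcome in turn. The ANOVA alternative also has two factors and no marker covariate. On that reading the selection wording is redundant, not a plan to adjust pain for markers. This largely stands: entry of markers is an inference from an internal conflict, not a stated step. It does not resolve the conflict, because the association aim still has no model that could deliver it, and it does not protect the treatment term.

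A reader might infer that the plan inflates the false-positive rate. Forcing treatment and marker together into every model does give about 12% (correlation 0.3) or 30% (0.5) at a 1.02 SD shift. The plan does not force them; it screens first, and rejection stays near 4%.

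A reader might also infer that power loss is certain because one comparator is a steroid. The documents do not support that. Of systemic effects, the Risks section says only: "Systemic side effects such as infection, increased blood glucose, hypercortisolism, and others are rarely seen". It is silent on serum inflammation markers. If the steroid lowered the markers more while PRP lowered pain more, power would not fall, though the coefficient would still be shifted (upwards, to as much as 2.55). Hypotheses 1 and 2 together do expect PRP to lower both pain and markers, which is the direction that costs power, but the size is unknown.

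**Conclusion.** The concern holds as a defect of specification. One selection procedure covers the randomised comparison and the association aim, and its predictor list contradicts the second aim. The firmer figure applies to the literal reading: about 12% of trials would lose the treatment term at the design effect, given 16 per arm, a two-sided test and a back-solved SD of 1.66. That figure treats the comparison as one change score per patient; the mixed model would give a somewhat different value.

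The marker-related figures are illustrative. Power of about 70% down to 32% requires that markers are admitted, that treatment moves them by 0.5 to 1.02 SD in the same direction as pain, and that they correlate 0.3 to 0.5 with pain change. The documents establish none of these values. They do not support a claim that the plan states it will adjust pain for post-injection markers, or that it raises the false-positive rate.

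**What to change.** Split the Data Analysis section into two analyses.

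1. **Treatment effect.** For each outcome, a fixed mixed model with treatment, visit, treatment-by-visit interaction and the baseline value of the outcome, all always kept in. No stepwise selection, and no covariate measured after injection. The interaction also makes the model match the sample-size target, which is a between-arm difference in change from first to last visit.
2. **Associations between changes.** Separate models, labelled exploratory, that use within-patient changes and always keep treatment arm. Their results do not feed back into the first analysis.

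This settles both readings at once. The cost is SAP wording and one extra set of exploratory models; no further data or patients are needed.

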#### Plan for measurement of these outcomes:

- The Primary outcome measures will be:
  - o Change in 7 point pain Visual Analogue Scale (VAS)
- Secondary outcome measures include:
  - Hip Disability and Osteoarthritis Outcome Score (HOOS)
    - Western Ontario and McMaster Universities Arthritis Index (WOMAC), calculated as a subscore of the HOOS
  - Patient Reported Outcome Measurement Information System (PROMIS) Global Health Scale
  - o Serum Biomarker analysis: IFN-g, IL-6, MCP-1, MIP-1b, IL-1b, TNF-alpha, high-sensitivity CRP, COMP
  - Change in Kellgren-Lawrence classification scores calculated from AP pelvis radiographs between pre-treatment and 1 year post-treatment

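### The trial is powered on the 12-month difference in VAS change, but the plan names no such contrast and its p=0.10 deletion rule does not exempt treatment

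*Combined protocol and SAP*

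**What the plan says.** The Data Analysis section bases the sample size on "a difference in the change in pain between the first and last visit of 1.7 units" on the 7-point scale, with 80% power and alpha 0.05. This gives 32 patients (16 per group), raised to 40 for 20% withdrawal. Follow-up is at 6 weeks and 3, 6 and 12 months (Follow-up Visits), so the last visit is at 12 months. That the difference is between arms follows from the per-group N and from Hypothesis 1.

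The same section then chooses a mixed-effects linear regression and says: "Independent variables in the model are treatment assignment and time". It continues with variable selection. First, "we will perform univariate and univariable models to explore the relative importance of each predictor variable". Then the significant variables enter a multivariable model, which is reduced by "dropping the highest non-significant variable (significance will be set at p=0.10) until only significant variables remain". Finally: "This will be repeated for each dependent variable".

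The Primary Outcome section names pain on the VAS, and the outcome measurement plan names change in VAS. Neither names a visit. Potential Pitfalls and Limitations adds that "an alternative approach would be a two-way repeat measures ANOVA", without naming an interaction or a contrast.

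**The concern.** There are two separate gaps, both affecting the primary outcome.

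**The powered quantity has no named test.** With pain score as the outcome, a between-arm difference in change from baseline to 12 months is a treatment-by-time effect. A model with treatment and time only gives one treatment coefficient, averaged over the visits in the model. Two analysts could follow the text faithfully and report different primary results from the same data. The stated 80% would apply to only one of them.

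**The selection rule does not protect treatment.** VAS is a dependent variable, and treatment is one of only two named independent variables. Read literally, treatment can be removed from the final VAS model. If it stays, it stays because its own p-value was below 0.10, so the retained estimate has been selected on its size. The plan does not say how the 0.10 retention level relates to the design alpha of 0.05.

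**Working it through.** **1. The plan's own figures.** 32/(1 - 0.20) = 40, as stated. N = 32 cannot be reproduced independently because no SD is given, so I solved for it. With 16 per arm, 30 df, two-sided 0.05 and 80% power, the noncentral t gives a standardised difference of 1.024, so SD of change = 1.7/1.024 = 1.66. The normal formula gives 1.72. The plan does not state sidedness; one-sided testing would imply 1.89 to 1.93. I use 1.66.

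**2. What the listed model estimates.** With complete, balanced data and a random intercept, the treatment coefficient is the difference between arms in patient averages.

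- Change scores: the mean effect over the four follow-up visits. It equals the powered 1.7 whenever that mean is 1.7. A constant effect is one such case; effects of 1.9, 1.5, 1.7 and 1.7 are another.
- Five raw visits including baseline, where the expected difference is zero: (0 + 4m)/5 = 1.7 requires m = 2.125, so the follow-up mean must be 1.25 times the 12-month effect.

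**3. Two illustrative profiles, both reaching 1.7 at 12 months.**

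- Linear growth: the mean of 1.5/12, 3/12, 6/12 and 12/12 is 0.47, so the effects are 1.7 x 0.47 = 0.80 (change scores) and 0.80 x 4/5 = 0.64 (five visits).
- Constant from 6 weeks: 1.70 and 1.70 x 4/5 = 1.36.

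**4. One case worked by hand.** Assume equal SDs and a correlation of 0.5 between all visits. The SD at each visit is then 1.66/sqrt(2 x 0.5) = 1.66. Power comes from the noncentral t with 30 df and noncentrality (effect/SD) x sqrt(16/2).

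- 12-month contrast: 1.7/1.66 x 2.83 = 2.90, power 80%.
- Average change: SD = 1.66 x sqrt(0.5 x 1.25) = 1.31. Linear: 0.80/1.31 x 2.83 = 1.72, power about 38%. Constant: 1.70/1.31 x 2.83 = 3.66, power about 94%.
- Five visits: SD = 1.66 x sqrt(0.5 + 0.5/5) = 1.29. Linear: 0.64/1.29 x 2.83 = 1.40, power about 28%. Constant: 1.36/1.29 x 2.83 = 2.99, power about 83%.

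**5. Range over assumptions.** I held the SD of change at 1.66 and varied the rest. Follow-up correlation was 0.3 to 0.7. Baseline SD was 0.5 to 1.0, with baseline-to-follow-up correlation 0.6 or 1.0 times the follow-up correlation. A further set used equal SDs and one common correlation at all visits.

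| Test | Linear growth | Constant effect |
|---|---|---|
| 12-month contrast | 80% | 80% |
| Average of four change scores | about 34-52% | about 91-99% |
| Average of five raw visits | about 15-48% | about 52-98% |

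**6. The deletion rule.** The chance that treatment is removed is 1 minus power at two-sided 0.10. With no true effect it is 1 - 0.10 = 90%. In the five-visit case of step 4 it is about 60% under linear growth and 10% under a constant effect.

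**The case against.** The best defence is that the text lists independent variables, not a model formula. The section says the mixed model is for following changes in each measure across the visits, the primary measure is itself a change, and a two-way repeated-measures ANOVA would normally carry an interaction. An interaction may well be intended. That much stands: the plan does not commit to an additive model, and a reader should not infer that it does. But no section states the interaction, and even an overall interaction test across five visits is not the 12-month contrast used for the sample size.

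The stepwise passage may also be meant for the exploratory aim, "as well as the associations between changes of multiple parameters". Screening many predictors fits that aim better than a model with two terms. This is plausible, but the section describes no separate confirmatory VAS model and extends the procedure to each dependent variable.

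The power figures rest on assumed inputs, and this stands too. Equal weighting of visits assumes a random intercept and complete data. Fixing 16 per arm ignores that 20 are randomised and that a mixed model uses early visits from patients who withdraw; with 20 complete per arm, change-score power under linear growth would be at most about 41-58%.

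Four stronger readings are tempting but not supported:

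- *The trial is underpowered.* Averaging can give more or less than 80%, depending on a time course that the documents do not give.
- *The coefficient is right only if the effect is constant.* Equality of the means in step 2 is enough.
- *No treatment estimate would exist after deletion.* The univariable estimate would remain.
- *The primary test is run at 10%.* The 0.10 is a retention level; the text does not say that retention counts as a positive result.

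**Conclusion.** The concern holds as under-specification of the primary analysis and needs correcting. The stated 80% belongs only to the 12-month contrast, and the plan does not name that contrast as its test. This part rests on the text alone.

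The deletion rule, read literally, makes the final VAS model depend on the data. Treatment leaves it in about 90% of trials if there is no effect. When treatment is retained with modest power, its estimate tends to be too large, but no general size can be given because that depends on the effect profile and the number analysed.

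The power ranges show only that the choice of test matters. They assume 16 analysed per arm, an SD of change of 1.66, a true 12-month difference of 1.7 and the covariance patterns listed, none of which the documents supply beyond the 16 and the 1.7.

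**What to change.** For VAS, prespecify one primary mixed model with treatment, categorical visit and treatment-by-visit. Make the 12-month between-arm difference in change, at two-sided 0.05, the primary test, so that it matches the existing power statement. Report the earlier visits as secondary results from the same model. State that these terms are fixed and exempt from the univariable screen and the p=0.10 removal, and label all stepwise modelling exploratory.

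If the team prefers the average over follow-up visits as the primary quantity, say so and restate the power for it.

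The cost is wording in one section. No new data or patients are needed, and N stays at 32 (40 with withdrawal). The downside is that, if the effect is constant over the year, the 12-month contrast has less power than the average of change scores (80% against about 91-99% under the assumptions above). It also relies more on attendance at 12 months.
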